## II. INTRODUCTION

Toothbrushes with tapered bristles were designed to clean plaque accumulated interdental area effectively. *In vitro* studies showed that the effectiveness in artificial plaque reduction is greater than that of the conventional toothbrushes with end rounded bristles. However, clinical studies in dental plaque and gingivitis have not showed consistent result in the superiority comparing to conventional toothbrushes. The purpose of this cross-over clinical research is to evaluate the cleaning efficacy of toothbrushes tufted with two types of tapered bristles and end rounded bristles in removal of interdental plaque with clinical measurement (Plaque Index) and objective measurement (digitally measured plaque area). This Proof of Concept study will demonstrate the influence by a type of processing bristles on removal of interdental plaque and determine an agreement between the different evaluation methods.

## III. STUDY OBJECTIVES

The primary objective of this study is to evaluate and compare toothbrushes with three different bristle types in the reduction of plaque index (**PI**) for interdental area and digitally measured interdental plaque area after one-time brushing.

Secondary objectives are to evaluate toothbrushes with three different bristle types in the changes of PI, digitally measured interdental plaque area and gingival abrasion one week after using the toothbrushes, and to assess an agreement between the different evaluation methods (**PI** and a plaque area by image analysis)

## IV. STUDY GROUPS

Three different bristles will be tufted into the same tuft pattern. All toothbrush head and handle are identical (Sonic TB without turning on the sonic vibration). The study samples will be provided by sponsor. The bristle dimensions (height, base diameter of filament) will be same. The difference of three toothbrushes is a type of processing bristles.

- A: Tapered bristles (double tapered J-hook)
- B: Tapered bristles (single tapered J-hook)
- C: End rounded bristles

Table 1. Physical characteristics of the bristles in all test groups

	Product A	Product B	Product C
Name	Double tapered J-hook (OTJ)	Single tapered J-hook (STJ)	End rounded (Control)

Version 061020

Individual filament heights in all tufts	10 and 13 mm	10 and 13 mm	13 and 13 mm
Tall filament end	Chemically tapered	Chemically tapered	Rounded
Short filament end	Chemically tapered	Rounded	Rounded
Filament's base diameter, milli inch (mm)	7 (0.18)	7 (0.18)	7 (0.18)
Filament material	PBT**	PBT**	Nylon

\*Pending, to check with supplier, \*\* Polybutylene terephthalate

[figure not shown]

Figure 1. Toothbrush head schematic showing tuft patterns (circles) used in all test groups

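### Control brush C is printed with a different filament material and height profile from A and B, so differences from C cannot be attributed to tapering

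*Combined protocol and SAP*

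**What the plan says.** Section IV describes three brushes with the same head, handle and tuft pattern. On the filaments it says "The bristle dimensions (height, base diameter of filament) will be same" and then "The difference of three toothbrushes is a type of processing bristles".

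Table 1 in that section lists five physical attributes. Base diameter agrees across the brushes, but two rows outside the filament ends do not. C has heights of 13 and 13 mm against 10 and 13 mm for A and B. In the row "Filament material", C is nylon and A and B are PBT. A footnote reads "Pending, to check with supplier", but no cell in the available text carries its mark.

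The Introduction gives two aims. One concerns whole brushes: "to evaluate the cleaning efficacy of toothbrushes tufted with two types of tapered bristles and end rounded bristles in removal of interdental plaque". The other is causal: "This Proof of Concept study will demonstrate the influence by a type of processing bristles on removal of interdental plaque". The primary objective in Section III is again at brush level: "evaluate and compare toothbrushes with three different bristle types in the reduction of plaque index".

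**The concern.** To attribute a difference between two brushes to the way the filaments are processed, the brushes must be alike in everything else that could affect plaque removal. Section IV reads as if that were so. Table 1 says otherwise for C, the end-rounded control and the reference for the tapered-versus-conventional question that opens the Introduction.

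Randomisation and the crossover do not help. They balance differences between subjects and periods, whereas material and height profile belong to the product and go wherever the product goes. No test named in Section XVI can separate attributes that always change together.

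The attribution is at stake in both directions. An advantage of A or B over C might come from tapering, from PBT or from the staggered heights. A null result might mean that tapering does nothing, or that another attribute offset it.

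**Working it through.** **Inputs (Section IV, Table 1, as printed)**

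| Attribute | A | B | C | Type |
|---|---|---|---|---|
| Heights (mm) | 10, 13 | 10, 13 | 13, 13 | not processing |
| Tall end | tapered | tapered | rounded | processing |
| Short end | tapered | rounded | rounded | processing |
| Base diameter | 7 milli inch | 7 milli inch | 7 milli inch | equal |
| Material | PBT | PBT | nylon | not processing |

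**The plan's own derived figure.** 7 × 0.0254 mm = 0.1778 mm, which rounds to the printed 0.18 mm. The diameter row is consistent and equal in all three brushes.

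**What each contrast contains.** Write the mean outcome of a brush as μ, plus *t* if the tall end is tapered, *s* if the short end is tapered, *m* if the material is PBT and *h* if the heights are 10/13. Then:

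- A = μ + t + s + m + h
- B = μ + t + m + h
- C = μ
- A − B = s
- B − C = t + m + h
- A − C = t + s + m + h

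A vs B isolates the short end. B vs C mixes three effects and A vs C mixes four. The columns for *t*, *m* and *h* are all (1, 1, 0) in the order A, B, C, so they are completely aliased. There are five parameters and the rank is 3. Three brushes can never give more than rank 3, so the rank adds nothing by itself; what matters is which effects share a column.

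**How this depends on the supplier check.** A and B are held as printed and C is varied:

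| C turns out to be | Non-processing differences (A−B / B−C / A−C) | All differing rows (A−B / B−C / A−C) | Parameters vs rank | Tall-end effect estimable? |
|---|---|---|---|---|
| nylon, 13/13 (printed) | 0 / 2 / 2 | 1 / 3 / 4 | 5 vs 3 | no |
| nylon, 10/13 | 0 / 1 / 1 | 1 / 2 / 3 | 4 vs 3 | no |
| PBT, 13/13 | 0 / 1 / 1 | 1 / 2 / 3 | 4 vs 3 | no |
| PBT, 10/13 | 0 / 0 / 0 | 1 / 1 / 2 | 3 vs 3 | yes |

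The short-end effect (A − B) is estimable in all four cases. The tall-end effect is estimable only if C matches A and B in both material and heights. Correcting the height entry alone leaves nylon against PBT, and both C contrasts stay confounded. These are counts of attributes and scenarios, not probabilities or measures of bias.

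**The case against.** The strongest reply has four parts.

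- **The height entry may be wrong.** Table 1 has a row "Short filament end" with an entry for C, which makes little sense if both C filaments are 13 mm. The text says heights are equal, and the footnote shows that something was still provisional. Height could also mean only the tallest filament, 13 mm in all three. This stands: the height row may be a misprint, and the B-vs-C row count is loosely defined if C has no shorter filament. The material row does not depend on it.
- **Material is disclosed and never said to be equal.** This is correct. The processing sentence does not say that processing is the only difference, so on material it is incomplete rather than contradicted. It still names one difference where the table shows another.
- **The study compares whole brushes.** Section III, the primary outcomes in Section XV and the first aim in the Introduction can all be met as the plan stands. This limits the point to the causal sentence in the Introduction and the description in Section IV. A vs B supports that causal sentence, but only for the short filament end.
- **It is a proof-of-concept study that already has a supplier check open.** Proof of concept is the stated reason for having no sample size calculation. It does not make an aliased contrast interpretable. The footnote shows that a check was intended; it does not say which entry it concerns or what follows from the answer.

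**Conclusion.** The concern holds. With Table 1 as printed, A vs C and B vs C are valid whole-brush comparisons but cannot be attributed to tapering. Each carries two non-processing differences, and only A vs B is matched. The nylon/PBT difference is sufficient by itself, so the conclusion survives a correction of the height entry. It falls only if C is confirmed to match A and B in both material and heights.

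This assumes that the printed A and B entries are right and that processing means the treatment of the filament ends, as Table 1 separates it from material and height. The documents give no figure for the effect of material or height profile on plaque removal, so neither the size nor the direction of any bias can be stated. The point should be fixed, but it does not undermine the primary objective.

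**What to change.** 1. Before the study starts, confirm with the supplier C's filament heights and material, and which Table 1 entry the footnote refers to. Reconcile the Section IV text, Table 1 and the footnote. Nothing here presumes which entry is right.
2. If C is confirmed to differ in material or height profile, replace the processing sentence in Section IV with:

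   > The brushes differ in filament-end processing; C also differs from A and B in [filament material] [and] [filament height profile].

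   Add to Section II:

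   > A vs C and B vs C compare whole brush configurations, in which processing is confounded with [material] [and] [height profile]; only A vs B isolates a processing difference (short filament end).

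   The C comparisons stay in the analysis; only their interpretation is narrowed.
3. If C matches in both, correct Table 1 and keep the processing claim. B vs C then isolates the tall end, A vs B the short end, and A vs C both together.
4. If any A or B entry changes, recheck that those two brushes are still matched.

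Section III needs no change. The cost is one supplier enquiry and a few lines of text, with no added subjects, visits, measurements or tests. If C does differ, the price is a narrower claim on tapered versus end-rounded bristles.

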## V. SUBJECT INFORMATION AND CONSENT

The clinical investigation, including the consent form, will be reviewed by an IRB in accordance with Title 21 of the Code of Federal Regulations, Parts 50 and 56. Subject consent will be obtained prior to participation in any study procedures as required by the Food and Drug Administration (FDA) GCP guidelines. Subjects will be given ample opportunity to read the consent form and to have all questions regarding study conduct answered prior to signing and dating the consent form. Each subject will be provided with an exact copy of the informed consent form to retain for his or her records.

Informed consent means the knowing consent of an individual, so situated so as to exercise free power of choice without undue inducement or constraint or coercion. The elements of information necessary for such consent include: a statement that the study involves research; an explanation of the procedures to be followed and their purpose; identification of any procedures that are experimental; any expected discomforts, risks or benefits; approximate number of subjects involved in the study; any appropriate alternative procedures or treatments; description of the confidentiality of subject records; name and phone number of the individual to contact with inquiries concerning the research; explanation of compensation or free medical treatment available for research-related injury; statement that the subject is free to withdraw consent and to discontinue participation at any time; statement that participation is voluntary; indication of any additional costs to the subject; assurance that the subject will be notified of new findings relevant to the subject's participation; statement that it is within the Principal Investigator's discretion to drop the subject from participation at any time.

In addition, the agreement entered into by the subject should include no exculpatory

Version 061020

language by which the subject is made to waive, or appear to waive, any of his/her legal rights or to release the institution from liability or negligence.

## VI. SUBJECT POPULATION

### **Number of Subjects**

A total number of 10 subjects will be enrolled. Volunteers must read and sign the Informed Consent Form after the nature of the study has been fully explained.

### **Inclusion Criteria**

Individuals may be included in the study provided they meet all of the following inclusion criteria:

- Must have read, understood and signed an informed consent prior to being entered into the study.
- Must be 18 to 70 years of age, male or female.
- Have at least 20 natural or restored teeth.
- Must have average Plaque Index of Ramfjord teeth at baseline greater than 2 (Quigley and Hein) at screening.
- Agree not to have a dental prophylaxis or any other elective, non-emergency dental procedures (other than those provided during the study) any time during the study.
- Agree to refrain from regular oral hygiene regimen for 24 hours and eating for 4 hours before the appointment in the study.
- Agree to abstain from the use of any dental products other than those provided in the study.
- Agree to comply with the conditions and schedule of the study.

### **Exclusion Criteria**

Individuals are not eligible for participation in this study if any of the following are noted:

- Physical limitations or restrictions that might preclude normal tooth brushing.
- Evidence of gross oral pathology
- Presence of severe gingivitis with 30 or more sites showing bleeding on probing.
- Evidence of major soft tissue lesions or trauma at the baseline visit as determined by the Investigator/Examiner.
- Chronic disease with concomitant oral manifestations
- Subjects who are currently undergoing, or require, extensive dental work, orthodontic treatment or periodontal surgery or orthodontic treatment in the preceding 3 months
- Currently using bleaching trays
- Eating disorders
- Recent history of substance abuse
- Smoking >10 cigarettes/day

Version 061020

- Participation in other clinical studies within 14 days of screening

## **VII. STUDY DESIGN OVERVIEW**

This cross-over group, examiner blinded, randomized, single center study will enroll subjects to target 10 subjects completing the study. Subjects will visit the clinical site 7 times including screening/enrollment visit. Subjects will be instructed to refrain from regular oral hygiene regimen for 24 hours and from eating for four hours before each appointment. The study examiner and staff will screen for subjects that meet the enrollment criteria. Subjects will be randomly assigned to one of three treatment groups. The study staff responsible for random assignments will be blinded to the product treatments.

- Group 1: A -> B -> C
- Group 2: B -> C ->A
- Group 3: C ->A-> B

After distribution of an assigned test toothbrush, subjects will receive a basic brushing instruction for Bass method by a study staff but without actual brushing. Subjects will perform toothbrushing using the assigned product for 2 minutes under supervision. Plaque Index (Navy PI), Gingival Abrasion Score and standardized digital dental photos will be taken before/after the one-time brushing.

Subjects will use the assigned toothbrush for a week until the next visit for evaluation. At the visit, the used toothbrush shall be returned to the study staff to avoid mixing up with next test product. PI and Gingival Abrasion Score will be recorded, and the standardized digital dental photos will be taken. After one week of wash-out period, subjects will return to the clinical site to start the next test product. The study schedule is showed in Table 2. Subjects will be instructed to keep a diary given by the study staff at Visit 1 throughout the study. Adverse experiences will be noted and recorded during the study.

Version 061020

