## **IX. TREATMENT REGIMEN**

Qualified subjects meeting all inclusion and exclusion criteria will be provided their assigned toothbrush (A, **B** or C) at Visit 2, 4 and 6 for use for immediate post-brushing evaluation and during the one-week treatment phase of the study. Subjects will be instructed to brush their teeth as instructed with their assigned toothbrush 2 times daily (after breakfast, before going to bed) for 2 minutes, using only the provided toothpaste for one-week study period.

Following their one week of use, they will then go through a one-week "washout" period and will follow their normal oral hygiene using study provided toothbrush and fluoride toothpaste. The same fluoride toothpaste will be used throughout the whole study period. Subjects will refrain from using other oral hygiene products throughout the study period.

Version 061020

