## **XII. STUDY PROCEDURE**

### **Screening and Enrollment Visit (Visit 1)**

Potential subjects will be instructed to refrain from regular oral hygiene regimen for 24 hours and eating for 4 hours before the appointment in the study.

Male and female subjects will read and sign the informed consent prior to enrollment. Subjects will be asked about demographics, medical history, general health status and current medication usage, and the information will be recorded.

Plaque Index (Quigley and Hein) of a whole mouth will be evaluated to verify that the subjects meet the inclusion and exclusion criteria (average PI>2).

If the participants meet the study criteria, they will be assigned to one of three treatment groups randomly based on computer generated randomized numbers.

Subjects will be instructed to use a toothpaste and a toothbrush (for wash-out period) provided by the study staff until the next visit. The appointment of next visit will be scheduled within 7 days ± one day.

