### **Visit 3**

After one week, subjects will return to the office to return the used toothbrush and their dairy. The following will happen at this visit:

The study staff will update of inclusion/exclusion criteria, medical history and concurrent medications. Adverse experiences will be noted and recorded during the study.

Whole-mouth Navy Plaque Index and Gingival Abrasion Score will be evaluated by a qualified examiner following visualize dental plaque and record. Then, standardized dental digital photographs of three close-up views of the retracted views: front, left and right lateral sides.

Subjects will follow their normal oral hygiene using a toothbrush and a toothpaste for "wash-out" period given at Visit 1.

Next appointment will be scheduled to return within 7 days  $\pm$  one day, and subjects will be instructed to refrain from regular oral hygiene regimen for 24 hours and eating for 4 hours before the appointment in the study.

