## **XV. EFFICACY**

### **Primary Outcome Variables**

The primary outcome variables to be assessed are:

- 1) the reduction of plaque index (Navy PI) for interdental area after one-time brushing in a whole mouth.
- 2) the reduction of digitally measured interdental plaque area on non-molar teeth, facial/buccal aspect after one-time brushing by image analysis.

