### **Secondary Outcome Variables**

- 1) the change of plaque index for interdental area in a whole mouth one week after using the toothbrushes.
- 2) the change of digitally measured interdental plaque area on non-molar teeth one week after using the toothbrushes.
- 3) correlation between plaque index and plaque area by image analysis in non-molar teeth, facial/buccal aspect.
- 4) The change of gingival abrasion score in whole mouth at one week after using the toothbrushes.

Version 061020

As necessary, additional exploratory statistical data analysis may be performed to further advance evaluation of the results.

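### Only the three cyclic brush orders are used; a balanced list of all six would be low-cost protection against carry-over in the one-week outcomes, and Section XVI should compare brushes within subject

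*Combined protocol and SAP*

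**What the plan says.** - **Orders.** Section VII: "Subjects will be randomly assigned to one of three treatment groups". The groups are A-B-C, B-C-A and C-A-B; ACB, BAC and CBA are not used, and no reason is given.
- **Allocation.** Section XII, Visit 1: "they will be assigned to one of three treatment groups randomly based on computer generated randomized numbers". Balance across groups is not mentioned.
- **Numbers.** Section VI: "A total number of 10 subjects will be enrolled". Section VII: the study "will enroll subjects to target 10 subjects completing the study". Section XIV says that withdrawals are not replaced.
- **Wash-out.** One week, in which subjects "will follow their normal oral hygiene using study provided toothbrush and fluoride toothpaste" (Section IX). The Visit 3 text reads "Next appointment will be scheduled to return within 7 days", with a one-day tolerance. Subjects also go 24 hours without oral hygiene before every appointment (Sections VI, VII and XII).
- **Outcomes.** The first primary outcome is "the reduction of plaque index (Navy PI) for interdental area after one-time brushing in a whole mouth"; the second is the matching reduction in digitally measured plaque area. The secondary outcomes include one-week changes in both plaque measures and "The change of gingival abrasion score in whole mouth at one week after using the toothbrushes".
- **Analysis.** Section XVI compares bristles by Student t or Wilcoxon rank sum test, with no subject, period or carry-over term. Its paired tests are only for before/after changes within one brush.

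**The concern.** The three orders balance brush against period, but not brush against the brush used before it. B never follows C, for instance, and A never follows B. Any brush-specific carry-over left after the wash-out therefore falls unevenly on the brush means. The awkward feature is that the third brush affects a comparison in which it plays no part: carry-over from C could make A and B look different when they are equal. A versus B is the contrast in which only the short filament end differs (Section IV, Table 1), while C also differs in material and in filament height.

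The analysis has a separate weakness. Unpaired tests discard the within-subject pairing that a cross-over is designed to supply.

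**Working it through.** The plan has no sample size, power or carry-over figure to reproduce.

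**Inputs.** The orders and the number of subjects come from Sections VI and VII. Carry-over is not in the documents and stays symbolic. I assume that the one-week change is taken from the same period's pre-brushing baseline. That baseline falls about one week after the previous brush stopped, and the one-week visit about two weeks after. Let c_X be carry-over from brush X at the one-week visit minus its carry-over at that baseline. R is the largest minus the smallest c.

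**Step 1: equal groups, by hand.** With three orders, each brush is used first by one third of subjects and follows one fixed brush in the other two thirds:
- A mean takes in (2/3)c_C, B mean (2/3)c_A, C mean (2/3)c_B.
- B − A takes in (2/3)(c_A − c_C). Brush B's own carry-over is absent and the third brush's is present.

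With six orders:
- A mean takes in (1/3)(c_B + c_C), and B mean (1/3)(c_A + c_C).
- B − A takes in (1/3)(c_A − c_B). Brush C cancels.

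**Step 2: 10 and 12 subjects.** Carry-over indicators were regressed on the subject + period + brush design. The worst bias of a contrast is the sum of its positive coefficients times R. Variances are in units of the error variance.

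| Design | Worst bias | Third-brush weight | Contrast variance | Variance if carry-over is fitted |
|---|---|---|---|---|
| 3 orders, n=10 (4/3/3) | 0.70R | 0.64-0.70 | 0.202 | 0.98-1.09 |
| 6 orders, n=10, one short order from each cyclic set | 0.375-0.40R | 0-0.075 | 0.200-0.206 | 0.235-0.276 |
| 6 orders, n=10, both short orders from one set | 0.434R | up to 0.172 | 0.202 | 0.249-0.270 |
| 3 orders, n=12 | 0.67R | 0.67 | 0.167 | 0.833 |
| 6 orders, n=12 | 0.33R | 0 | 0.167 | 0.208 |

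The cyclic sets are {ABC, BCA, CAB} and {ACB, BAC, CBA}; a short order is one given to a single subject.

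**Step 3: what might R be?** Assumption: a fraction f of the previous brush's effect remains after each week. The change score then carries f² − f, in size f(1 − f): 0.09 at f = 0.1 or 0.9, and at most 0.25 at f = 0.5. Suppose two brushes are equal and the third differs by D after a week of use. At f = 0.5 the false difference at n=10 is 0.25 × (0.64 to 0.70) = 0.16-0.17D with three orders. With six orders (one short order from each set) it is 0.25 × (0 to 0.075) = 0-0.02D. If D is one within-subject SD, a carry-over of 0.25 SD gives a paired 5% t test a false-positive rate of about 6% with three orders and about 5% with six (simulation).

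**Step 4: unpaired against paired.** Assumptions: n=10, within-subject correlation 0.5, a true difference of 1 SD of a single measurement, no carry-over.
- The true SE of the difference is √(2(1 − 0.5)/10) = 0.316.
- The unpaired test uses √(2/10) = 0.447 on average, too large by a factor of 1.41.
- The unpaired false-positive rate is about 1% instead of 5%, and power about 59% instead of 80%.

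**The case against.** The plan has real safeguards. All subjects spend the wash-out on a common brush and toothpaste, period 1 also starts after such a week, and every visit follows 24 hours without oral hygiene, so plaque at each visit includes a standard regrowth. This does not prove that carry-over is zero, and it says less about gingival abrasion, but it makes a large plaque carry-over unlikely. That stands.

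The scope is also narrow. The primary outcomes are pre-to-post reductions within one visit and are largely protected. What remains is three secondary change scores in a 10-subject proof-of-concept study.

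Three stronger readings are tempting and unsupported:
- *A and B will be falsely separated, with false-positive rates of 19-46%.* Those paired-test rates need a carry-over of 1 to 1.5 within-subject SD. Under the decay assumption, where at most 0.25 is carried, the previous brush's effect would have to differ by at least 4 to 6 SD. Nothing in the documents suggests this.
- *Three orders confound carry-over beyond recovery.* It can be estimated, but at a 4.9- to 5.4-fold variance, against 1.2- to 1.4-fold with six orders.
- *Six orders remove the problem.* They nearly do so for two brushes with equal carry-over. In general the worst bias is only cut by 43-46% at n=10, or by half at n=12. If one brush alone has carry-over L, one contrast goes from 0-0.03L to 0.25-0.40L at n=10. If that brush is C, the contrast is B − C, tapered against control. The other two improve, from 0.64-0.70L to 0.25-0.40L and to 0-0.075L.

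**Conclusion.** Worth considering, not a demonstrated error. The succession imbalance is plain in Section VII and no other part of the plan addresses it. The size of any bias is unknown because carry-over is not sized; the coefficients assume first-order carry-over and a change from the same period's baseline. For the one-week changes, six orders lower the worst bias from 0.70R to 0.375-0.40R at n=10, with a contrast variance of at most 0.206 against 0.202. They also make a carry-over sensitivity analysis affordable. If there is no carry-over, the change gains nothing and costs almost nothing.

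The unpaired between-brush tests are a separate weakness. It holds whichever orders are used and does not depend on carry-over; its size depends on the within-subject correlation, assumed to be 0.5 above.

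**What to change.** 1. **Settle the number first.** Reconcile 10 enrolled (Section VI) with 10 completing (Section VII) before the list is made.
2. **Section VII.** Randomise to ABC, BCA, CAB, ACB, BAC and CBA from a pre-generated balanced list. With 10 subjects use 2/2/2/2/1/1, taking one single-subject order from each cyclic set, for example ABC and BAC. With 12, use two per order. Simple unrestricted randomisation would not do: over 10 subjects it removes the third-brush bias only on average. If three orders are kept, state a 4/3/3 list (4/4/4 with 12).
3. **Section XVI.** Replace the Student t and rank sum between-brush tests with a model containing subject, period and brush. Fit carry-over only as a sensitivity analysis. The period term is needed because an incomplete set of orders leaves a slight period imbalance.

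**Cost.** A new list, three more lines in Section VII and one rewritten paragraph in Section XVI; no extra subjects, visits or products. The price is the contrast that can get worse, described above. Unreplaced withdrawals can also empty a single-subject order. After one loss from 10, the worst bias is 0.39-0.54R over all fifteen possible six-order lists, against 0.67-0.74R with three orders, and the variance is 0.222-0.244 against 0.222-0.231.
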